6.3.1. Patient Numbering

Each patient is identified in the study by a Patient Number (Patient No.) that is assigned when the patient is first enrolled for screening and is retained as the primary identifier for the patient throughout his/her entire participation in the study. The Patient No. consists of the 4 digits Center Number (as assigned by the Sponsor or designee to the investigative site) with a sequential patient number suffixed to it (the last 4 digits of the Patient ID), so that each patient is numbered uniquely across the entire database. Upon signing the screening informed consent form, the patient is assigned to the next sequential Patient No. available to the Investigator through IWRS. Once assigned, the Patient No. must not be reused for any other patient and the Patient No. for that individual must not be changed, even if the patient is re-screened. If the patient fails to be randomized or start treatment for any reason, the reason will be entered into the eCRF. Refer to [Section 5.4](#) for further information on data collected for screen failures. IWRS must be notified within 2 days that the patient was not randomized.

6.4. Study Treatment Compliance

Compliance with all study-related treatments will be emphasized to the patient by the site personnel, and appropriate steps should be taken to optimize compliance during the study. Patient compliance with study treatment will be assessed at each visit. Compliance will be assessed by an accounting of returned study drug, patient interviews and a review of patient diary entries. Patients will be instructed to bring all study drugs with them to the study visits in order for site personnel to assess study drug accountability. Deviation(s) from the prescribed dosage regimen will be recorded in the eCRF.

In the case of overdosage of encorafenib or binimetinib, see [Section 7.6](#). There is no known antidote for overdosage of encorafenib or binimetinib. Supportive care should be instituted.

6.5. Concomitant Therapy

All concomitant medications and treatments (including over-the-counter or prescription medicines, vitamins, vaccines and/or herbal supplements) must be recorded in the eCRF. Details regarding all prior anticancer treatment will also be recorded in the eCRF.

Any medication received within 28 days before the first dose of study treatment and within 30 days after the last dose of study treatment, or until the patient begins a new anticancer therapy, whichever occurs first, will be recorded in the eCRF. Any addition, deletion or change in the dose of these medications will also be recorded. Details of prior antineoplastic treatments including number of prior metastatic regimens will also be recorded. Unless specifically prohibited, concomitant medications may be administered at the Investigator's discretion to manage the patient's medical condition and to conform to standard practice during the Treatment Period.

Any medication or vaccine (including over-the-counter or prescription medicines, vitamins and/or herbal supplements) that the patient is receiving at the time of enrollment or receives during the study must be recorded along with:

- Reason for use.
- Dates of administration including start and end dates.

- Dosage information (using generic drug names when possible), including dose and frequency.

The Sponsor Medical Monitor should be contacted if there are any questions regarding concomitant or prior therapy.

6.5.1. Permitted Concomitant Therapy Requiring Caution and/or Action

6.5.1.1. CYP and UGT Substrates and Inhibitors

Encorafenib is a reversible inhibitor of CYP2B6, CYP2C9, CYP3A4 and UGT1A1. It is also a time-dependent inhibitor of CYP3A4 and induced CYP2B6, CYP2C9 and CYP3A4 in human primary hepatocytes. Permitted medications to be used with caution in this study include those that are sensitive substrates of CYP2B6, CYP2C9, CYP3A4 and UGT1A1 or those substrates that have a narrow therapeutic index.

There is a potential for encorafenib to induce CYP3A4, which may reduce the effectiveness of hormonal contraception methods. Therefore, the use of at least 1 form of non-hormonal contraception is required for females of childbearing potential during participation in this study. Caution should be used in patients receiving concomitant treatment with other drugs that are substrates of CYP3A4 as the efficacy of these drugs could be reduced when administered with encorafenib.

Encorafenib has been identified as being metabolized by CYP3A4 and to a lesser extent by CYP2C19 in vitro. Concomitant use of moderate CYP3A4 inhibitors should be avoided. If use of a moderate CYP3A4 inhibitor is unavoidable, short-term use (≤ 30 days) following discussion with the Sponsor may be permitted with an accompanying dose reduction to one-half of the encorafenib dose prior to use of the moderate CYP3A4 inhibitor (i.e., for the standard-dose treatment arm, 225 mg encorafenib QD, and for the high-dose treatment arm, 150 mg encorafenib BID). After the inhibitor has been discontinued for 3 to 5 elimination half-lives, resume the encorafenib dose that was taken prior to initiating the CYP3A4 inhibitor.

In vitro, binimetinib has been identified to be primarily metabolized by glucuronidation. Strong inducers of UGT1A1 should be taken with caution when co-administered with binimetinib.

For tabulated CYP substrates, inhibitors and inducers to be used with caution or avoided, please consult the FDA website: [Drug Development and Drug Interactions: Table of Substrates, Inhibitors and Inducers](#).

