4. STUDY DESIGN

4.1. Overall Design

This is a multicenter, randomized open-label Phase 2 study to assess the safety, efficacy and PK of 2 dosing regimens of encorafenib + binimetinib combination therapy in patients with *BRAFV600*-mutant melanoma with asymptomatic brain metastasis. Approximately 110 eligible patients will be enrolled, including 9 patients in a single-arm Safety Lead-in. After a Screening Period, treatment will be administered in 28-day cycles and will continue until disease progression, unacceptable toxicity, withdrawal of consent, start of subsequent anticancer therapy, death. Once the patient discontinues study treatment, the Treatment Period will end, and the patient will enter the Follow-up Period. The 2 doses of encorafenib + binimetinib combination treatment to be evaluated are summarized in Table 5.

The first 9 evaluable patients in the high-dose treatment will constitute the high-dose Safety Lead-in cohort. Evaluable patients for the Safety Lead-in cohort must have experienced:

- either a DLT (Table 7) or
- received at least 75% of the planned cumulative dose of both study drugs during Cycle 1.

If the high-dose treatment is found safe during the Safety Lead-in, based on predefined evaluation criteria (Section 6.6), eligible patients will be randomized (1:1; approximately 50 patients in each treatment arm) to the standard-dose (Arm A) or high-dose (Arm B) treatment arm stratified by:

- baseline number of brain metastases (1 to 2 brain lesions vs. ≥ 3 brain lesions at baseline assessment) and
- history of prior local therapy [e.g., SRS or SRT (yes vs. no)].

Table 5. Planned Treatment Arms

Treatment Arm	Encorafenib Dose	Binimetinib Dose
A (standard-dose) ¹	450 mg QD	45 mg BID
B (high-dose)	300 mg BID	45 mg BID

1. The standard dose arm (Arm A) includes patients who have intra-patient dose escalation (see Section 6.7.2).

If the high-dose treatment is determined not to be safe in the Safety Lead-in, no patients will be enrolled into Arm B, and up to 100 patients will be enrolled into 2 cohorts in the standard-dose Arm A:

- **Cohort 1:** Up to 50 patients with *BRAFV600* cutaneous melanoma with metastases to the brain confirmed by MRI, asymptomatic, and with prior local therapy (e.g., SRS or SRT).

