6.7. Dose Modification

6.7.1. General Procedures for Dose Modification

Treatment with encorafenib and binimetinib may be delayed, allowing for resolution of toxicity. Patients may resume treatment if no medical condition or other circumstance exists that, in the opinion of the Investigator, would make the patient unsuitable for further participation in the study. Patients should resume study treatment within 2 weeks of the scheduled interruption, unless otherwise discussed with the Sponsor. The Investigator should contact the Sponsor Medical Monitor to discuss the case of any patient whose treatment has been delayed for more than 2 weeks (14 days) before restarting study treatment.

Instructions for dose modifications and interruptions are outlined in [Appendix 2](#) (encorafenib) and [Appendix 3](#) (binimetinib). Individual decisions regarding dose interruptions and modifications should be made using appropriate clinical judgment in consultation with the Sponsor Medical Monitor, considering relatedness of the AE to the study treatment and the patient's underlying condition. Adverse events that have a clear alternative explanation, or transient (≤ 72 hours) abnormal laboratory values without associated clinically significant signs or symptoms may be exempt from dose-reduction rules as clinically appropriate. Dose interruptions are permitted in the case of medical or surgical events or logistical reasons not related to study treatment (e.g., elective surgery, unrelated medical events, patient vacation, holidays). The reason for interruption will be documented in the patient's study record. All dose modifications are based on the worst preceding toxicity.

Doses of encorafenib and binimetinib may be independently delayed and reduced for toxicity management as outlined in [Table 8](#). The Investigator should refer to and follow the labeled guidance (if applicable) and/or institutional guidelines for the management of toxicities relating to encorafenib and binimetinib. Detailed guidelines can also be found in [Appendix 2](#) and [Appendix 3](#).

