When the AE that resulted in a dose reduction improves to and remains stable to the patient's baseline for a minimum of 14 days, the dose can be re-escalated up to the starting dose level (450 mg encorafenib QD plus 45 mg binimetinib BID) at the discretion of the Investigator, provided there are no other concomitant toxicities that would prevent drug re-escalation. There is no limit to the number of times the patient can have their dose reduced or re-escalated; however:

- No dose re-escalation of encorafenib is allowed after a dose reduction due to prolonged QTcF \geq 501 msec;
- No dose re-escalation of binimetinib is allowed after a dose reduction due to LVEF dysfunction;
- No dose re-escalation of binimetinib or encorafenib is allowed after a dose reduction due to ocular toxicity \geq Grade 2.
- Patients who are receiving 600 mg encorafenib QD plus 45 mg binimetinib BID who require a dose reduction are not permitted to re-escalate (see [Section 6.7.2](#)).

Table 8. Dose Reductions for Encorafenib and Binimetinib

Level	Dose
Dose Reduction for Encorafenib in the High-dose Combination Arm	
0 (starting dose)	300 mg BID
-1	225 mg BID
-2	150 mg BID
-3	75 mg BID ^a
Dose Reduction for Encorafenib in the Standard-dose Combination Arm	
0 (starting dose)	450 mg QD
-1	300 mg QD
-2	225 mg QD ^b
Dose Reduction for Single-agent Encorafenib^c	
-1	300 mg QD
-2	225 mg QD ^b
Dose Reduction for Binimetinib (both arms)	
0	45 mg BID
-1	30 mg BID ^d

Table 8. Dose Reductions for Encorafenib and Binimetinib

Level	Dose
-------	------

NOTE: Dose reduction is based on the highest AE grade.

- a. Dose reduction below 75 mg BID is not allowed.
- b. Dose reduction below 225 QD is not allowed.
- c. Single-agent encorafenib dose reduction applies to patients who have permanently discontinued binimetinib.
- d. Dose reduction below 30 mg BID is not allowed.

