If a patient misses > 28 consecutive days of dosing with combination treatment (both encorafenib and binimetinib), study treatment will be discontinued unless, in the opinion of the Investigator, the patient will derive clinical benefit from continued treatment. The Investigator will discuss this decision with the Sponsor Medical Monitor. If a patient permanently discontinues binimetinib (i.e., no dose for > 28 days), the patient may continue single-agent encorafenib if, in the opinion of the Investigator, the patient is deriving clinical benefit. Doses of single-agent encorafenib are decreased to a maximum of 300 mg QD when binimetinib is permanently discontinued.

If a patient permanently discontinues treatment with encorafenib, he or she must discontinue treatment with binimetinib.

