6.7.2. Intra-Patient Dose Escalation of Encorafenib

During the Phase 2 part of the study, all patients will begin treatment with standard doses of encorafenib (450 mg QD) plus binimetinib (45 mg BID). Patients who are able to tolerate the standard dose of encorafenib (450 mg QD) plus binimetinib (45 mg BID) during the first 4 weeks of treatment (Cycle 1) should be dose-escalated to 600 mg encorafenib QD plus 45 mg binimetinib BID provided the following criteria are met:

- Must not have experienced a clinically meaningful treatment-related adverse event of CTCAE \geq Grade 2 that based on investigator assessment prohibits escalation.
- Requires no dose reductions during the first 4 weeks (Cycle 1; guidelines for dose reductions are detailed in [Appendix 2](#) for encorafenib and [Appendix 3](#) for binimetinib). However, a single dose interruption of up to 4 days is permitted during Cycle 1. To ensure steady state exposures of encorafenib + binimetinib in patients undergoing intra-patient dose escalation, 7 days of consecutive dosing at the starting doses (450 mg QD encorafenib + 45 mg BID binimetinib) are required prior to the intra-patient escalation (600 mg QD encorafenib + 45 mg BID binimetinib).

Therefore, intra-patient dose escalation should occur on Cycle 2 Day 1 (+ 7 days).

Investigators must confirm patients meet all criteria to qualify for dose escalation. Patients who cannot tolerate 600 mg QD encorafenib plus 45 mg BID binimetinib will be dose reduced to 450 mg QD encorafenib plus 45 mg BID binimetinib. Re-escalation up to 600 mg QD will not be permitted. Additional dose delays or reductions will be permitted for toxicity management as outlined in [Table 8](#).

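### The half-dose figures given for moderate CYP3A4 inhibitor use (Protocol 6.5.1.1) are right only at the starting doses, and at some reduced doses one-half cannot be made from whole capsules

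*Protocol*

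**What the plan says.** Protocol Section 6.5.1.1 says that moderate CYP3A4 inhibitors should be avoided. If one cannot be avoided, up to 30 days of use may be permitted after discussion with the Sponsor, with "an accompanying dose reduction to one-half of the encorafenib dose prior to use of the moderate CYP3A4 inhibitor". A parenthesis opening with 'i.e.' then fixes the result by arm: "for the standard-dose treatment arm, 225 mg encorafenib QD", and 150 mg BID in the high-dose arm. Once the inhibitor has cleared, the patient goes back to whatever dose preceded it.

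The standard-dose arm is not a single dose. Table 5, footnote 1 states: "The standard dose arm (Arm A) includes patients who have intra-patient dose escalation". Under Section 6.7.2, patients who tolerate Cycle 1 "should be dose-escalated to 600 mg encorafenib QD plus 45 mg binimetinib BID provided the following criteria are met". Table 8, under "Dose Reduction for Encorafenib in the Standard-dose Combination Arm", adds levels of 300 and 225 mg QD, with the footnote "Dose reduction below 225 QD is not allowed". For the BID regimen Table 8 lists 300, 225, 150 and 75 mg.

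Table 6 lists one encorafenib strength, a 75 mg capsule, and Section 6.1 requires capsules to be swallowed whole.

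**The concern.** The rule follows the dose the patient is actually taking. The parenthesis follows the arm. Because 'i.e.' restates a rule rather than giving an example, a site may take 225 mg QD as the dose for any Arm A patient. That is wrong at every level except 450 mg. The 600 mg level is no rarity by design: it is the intended next step for patients who tolerate Cycle 1, and according to SAP Section 2 Phase 2 went ahead in the standard-dose arm only.

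What is at stake is a wrong dose for an individual patient during a short course of an interacting drug. At 600 mg the figure cuts the dose by more than the rule does. At 300 and 225 mg it cuts by less, in patients who have usually been reduced already for toxicity.

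**Working it through.** **Inputs.** Rule: new dose = prior dose / 2 (Section 6.5.1.1). Stated figures: 225 mg QD and 150 mg BID (same section). QD levels: 450 mg (Section 6.1), 600 mg (Section 6.7.2), 300 and 225 mg (Table 8). BID levels: 300, 225, 150 and 75 mg (Table 8). Capsule: 75 mg, taken whole (Table 6, Section 6.1).

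**Reproducing the stated figures.** 450 / 2 = 225 mg QD and 300 / 2 = 150 mg BID. Both come from the starting doses and from no other level.

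**Every level.** Capsules = (prior dose / 2) / 75. Share = stated figure / prior dose. BID rows are per dose.

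| Prior dose | Rule (one-half) | Capsules | Stated figure | Figure as share of prior dose |
|---|---|---|---|---|
| 600 mg QD | 300 mg | 4 | 225 mg | 37.5% |
| 450 mg QD | 225 mg | 3 | 225 mg | 50% |
| 300 mg QD | 150 mg | 2 | 225 mg | 75% |
| 225 mg QD | 112.5 mg | 1.5 | 225 mg | 100% |
| 300 mg BID | 150 mg | 2 | 150 mg | 50% |
| 225 mg BID | 112.5 mg | 1.5 | 150 mg | 66.7% |
| 150 mg BID | 75 mg | 1 | 150 mg | 100% |
| 75 mg BID | 37.5 mg | 0.5 | 150 mg | 200% |

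**Reading the table.** The figure equals one-half at one of four QD levels and one of four BID levels. Two different faults appear:

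- At 600 mg QD, 300 mg QD and 150 mg BID the figure is wrong, but the rule gives whole capsules and can be followed.
- At 225 mg QD, 225 mg BID and 75 mg BID the rule cannot be met with whole capsules. The stated figure does not help: it gives no reduction at 225 mg QD, too small a reduction at 225 mg BID, and twice the current dose at 75 mg BID.

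**Table 8 minimum.** One-half of 300 mg QD is 150 mg, which is 225 - 150 = 75 mg below the QD minimum. Section 6.7.1 introduces Table 8 with "Doses of encorafenib and binimetinib may be independently delayed and reduced for toxicity management", so the minimum appears to be a limit on toxicity reductions. Section 6.5.1.1 does not say so, and the footnote itself carries no qualification.

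**The case against.** The best defence is that the governing sentence is clear. Both the halving rule and the resumption rule refer to the patient's own dose, and elsewhere the protocol uses 'standard dose' to mean 450 mg QD (Sections 6.1 and 6.7.2, Table 6). On that reading the parenthesis only works the rule through for the two assigned doses. Use is also tightly controlled: avoidance is the default, 30 days is the limit, and the Sponsor is consulted first and may refuse.

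Much of this stands. A reader might infer that no usable dose exists anywhere away from 450 mg. The documents do not support that, since the rule works at 600 and 300 mg QD. The controls make an error less likely. They do not supply a dose, and the half-dose is the stated condition of permission, so where it cannot be made from capsules the text leaves a gap. Nor can the starting-dose reading be assumed, because Table 5, footnote 1 expressly places escalated patients in Arm A.

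Two other inferences should be resisted. One is that Table 8 forbids 150 mg QD: its stated purpose is toxicity management, so the 75 mg shortfall carries little weight and a clarifying note is enough. The other is that patients without binimetinib are a separate problem. Section 6.7.1 says: "Doses of single-agent encorafenib are decreased to a maximum of 300 mg QD when binimetinib is permanently discontinued". The single-agent levels in Table 8 are therefore 300 and 225 mg QD, and those rows of the table above already cover them.

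**Conclusion.** The point holds as a minor error in a dosing instruction. The parenthesis in Section 6.5.1.1 is correct only at 450 mg QD and 300 mg BID. In Arm A the stated dose is 75 mg too low at 600 mg QD (300 - 225) and 75 mg too high at 300 mg QD (225 - 150). At 225 mg QD neither the rule nor the figure gives a reduced dose that can be taken. The BID levels share the fault but matter less, because the high-dose arm was not opened in Phase 2 and only Safety Lead-in patients take that regimen.

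This rests on taking 'i.e.' at its ordinary meaning and on 75 mg being the only capsule strength, as Table 6 shows. A reader might go on to infer overexposure, harm or a biased efficacy result. The documents support none of these. They give no change in encorafenib exposure under a moderate inhibitor, and they do not say how many patients would need one. The primary endpoint, power and alpha are unaffected.

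**What to change.** In Protocol Section 6.5.1.1, replace the parenthesis with doses by current level:

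- QD: 600 to 300 mg, 450 to 225 mg, 300 to 150 mg.
- BID: 300 to 150 mg, 150 to 75 mg.
- Where one-half is not a whole number of capsules (225 mg QD, 225 mg BID, 75 mg BID): the moderate inhibitor is not to be used unless encorafenib is held.

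Add a short note that the Table 8 minimum doses apply to reductions for toxicity, so that 150 mg QD is not read as barred. The sponsor's clinical team should confirm that 150 mg QD is acceptable for this temporary use.

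The cost is a few sentences in one section. No data collection, sample size or SAP analysis changes.

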6.5.1.2. Transporter Substrates and Inhibitors

In vitro data showed that encorafenib is a substrate of the transporter P-gp. Thus, drugs that are known to inhibit or induce P-gp should be used with caution. Encorafenib is also a potent inhibitor of the renal transporters OAT1, OAT3 and OCT2, and the hepatic transporters OATP1B1 and OATP1B3. The co-administration of drugs that are known to be sensitive or narrow therapeutic index substrates of OAT1, OAT3, OCT2, OATP1B1 or OATP1B3 should be used with caution.

Binimetinib has also been shown to be a substrate of P-gp and BCRP. It is advised that inhibitors and inducers of P-gp and BCRP transporters should be taken with caution when co-administered with binimetinib.

For tabulated transporter substrates, inhibitors and inducers to be used with caution, please consult the FDA website: Drug Development and Drug Interactions: Table of Substrates, Inhibitors and Inducers.

6.5.1.3. Drugs with a Known Conditional or Possible Risk to Prolong QT Interval and/or Induce Torsade de Pointes

Investigators should use caution when administering encorafenib with concomitant medications with a known, conditional or possible risk to prolong the QT interval and/or induce torsade de pointes. Patients receiving such medications must be carefully monitored for potentiating of toxicity due to any individual concomitant medication and may require dose titration of the concomitant medication. See the CredibleMeds® website: [Combined List of Drugs That Prolong QT and/or cause Torsades de Pointes \(TDP\)](#).

6.5.2. Prohibited Concomitant Therapy

Medications specified below are not allowed during the study. If there is a clinical indication for one of these medications specifically prohibited during the study, discontinuation from the study treatment may be required. Patients may receive other medications that the Investigator deems to be medically necessary. The Investigator should discuss any questions regarding medications with the Sponsor. The final decision on any supportive therapy rests with the Investigator and/or the patient's primary physician. The decision to continue the patient in the study requires mutual agreement of the Investigator, the Sponsor and the patient.

The following therapies are prohibited during the Screening and Treatment Periods of this study (unless otherwise noted).

- No additional anticancer agents such as cytotoxic chemotherapy, small-molecule targeted agents, biological agents, immune response modifiers or hormonal therapy are to be administered to patients while they are receiving study treatment.
- Investigational drugs and devices.
- Radiation therapy (not including palliative radiotherapy at focal sites that covers $\leq 10\%$ of the bone marrow reserve).

Note: Palliative radiation therapy to target lesions is prohibited. Administration of palliative radiation therapy will be considered clinical progression for the purposes of determining PFS.

- Concomitant strong systemic CYP3A4 inhibitors, which could significantly increase the exposure of encorafenib.
- Concomitant moderate or strong systemic CYP3A4 inducers, which could significantly decrease the exposure of encorafenib.

No therapies are prohibited during the post-treatment Follow-up Period.

